#### 7.1.4.1.1 Initial Tumor Imaging

Initial tumor imaging at screening must be performed within 28 days prior to the date of allocation. The site study team must review screening images to confirm the subject has measurable disease per RECIST 1.1. Prior to allocation, the screening images must be submitted to M.D. Anderson radiology for confirmation of measurable disease per RECIST 1.1.

Scans performed as part of routine clinical management are acceptable for use as screening tumor imaging if they are of diagnostic quality, were performed within 28 days prior to the date of allocation, and can be assessed by M.D. Anderson radiology .

# Proprietary Information of MD Anderson

Protocol # 2016-0251

Date: February 24, 2020

92

## 7.1.4.1.2 Tumor Imaging During the Trial

The first on-trial imaging assessment should be performed at 9 weeks (63 days  $\pm$ 7 days) from the date of allocation. Subsequent tumor imaging should be performed Q9W (63 days  $\pm$ 7 days) or more frequently if clinically indicated. Imaging timing should follow calendar days and should not be adjusted for delays in cycle starts. Imaging should continue to be performed until disease progression or notification by Merck, whichever occurs first. All supplemental imaging, done outside from M.D. Anderson, must be submitted to M.D. Anderson radiology for retrospective review.

Per RECIST 1.1, PR and CR should be confirmed by a repeat tumor imaging assessment obtained 4 weeks or longer from the date the response was first documented. The tumor imaging performed to confirm a response may be performed, at the earliest, 4 weeks after the first indication of a response, or at the next scheduled scan (ie, 9 weeks later), whichever is clinically indicated. Subjects will then return to regular scheduled imaging Q9W (63 days  $\pm$ 7 days), starting with the next scheduled imaging time point. Subjects who obtain a confirmation scan do not need to undergo the next scheduled tumor imaging if it is 4 weeks later; tumor imaging may resume at the subsequent scheduled imaging time point.

Per iRECIST (Section 7.1.4.1.5), disease progression should be confirmed by the site 4 to 8 weeks after site-assessed first radiologic evidence of PD in clinically stable subjects. Subjects who have unconfirmed disease progression may continue on treatment at the discretion of the site Investigator until progression is confirmed by the site provided they have met the conditions detailed in Section 7.1.4.1.5. Subjects who receive confirmatory imaging do not need to undergo the next scheduled tumor imaging if it is less than 4 weeks later; tumor imaging may resume at the subsequent scheduled imaging time point if clinically stable. Subjects who have confirmed disease progression by iRECIST, as assessed by the site, will discontinue trial treatment. Exceptions are detailed in Section 7.1.4.1.5.

## 7.1.4.1.3 End of Treatment and Follow-up Tumor Imaging

In subjects who discontinue trial treatment, tumor imaging should be performed at the time of treatment discontinuation ( $\pm$ 4 week window). If a previous scan was obtained within 4 weeks prior to the date of discontinuation, then a scan at treatment discontinuation is not mandatory. In subjects who discontinue trial treatment due to documented disease progression, this is the final required tumor imaging.

In subjects who discontinue trial treatment without documented disease progression, every effort should be made to continue monitoring their disease status by tumor imaging using the same imaging schedule used while on treatment (every 63 days  $\pm$ 7 days) to monitor disease status until the start of a new anticancer treatment, disease progression, pregnancy, death, or the end of the trial, whichever occurs first.

# Proprietary Information of MD Anderson

Protocol # 2016-0251

Date: February 24, 2020

93

## 7.1.4.1.4 RECIST 1.1 Assessment of Disease

RECIST 1.1 will be applied by M.D. Anderson investigators as the primary measure for assessment of tumor response, date of disease progression, and as a basis for all protocol guidelines related to disease status (eg, discontinuation of trial therapy). Although RECIST 1.1 references a maximum of 5 target lesions in total and 2 per organ, Merck allows a maximum of 10 target lesions in total and 5 per organ, if clinically relevant to enable a broader sampling of tumor burden.

## 7.1.4.1.5 iRECIST Assessment of Disease

iRECIST is based on RECIST 1.1, but adapted to account for the unique tumor response seen with immunotherapeutic drugs. iRECIST will be used by the Investigator to assess tumor response and progression, and make treatment decisions. When clinically stable, subjects should not be discontinued until progression is confirmed by the Investigator, working with local radiology, according to the rules outlined in Section 12.2. This allowance to continue treatment despite initial radiologic PD takes into account the observation that some subjects can have a transient tumor flare in the first few months after the start of immunotherapy, and then experience subsequent disease response. This data will be captured in the clinical database.

Clinical stability is defined as the following:

- Absence of symptoms and signs indicating clinically significant progression of disease
- No decline in ECOG performance status
- No requirements for intensified management, including increased analgesia, radiation, or other palliative care

Any subject deemed **clinically unstable** should be discontinued from study treatment at site-assessed first radiologic evidence of PD, and is not required to have repeat tumor imaging for confirmation of PD by iRECIST.

If the Investigator decides to continue treatment, the subjects may continue to receive study treatment and the tumor assessment should be repeated 4 to 8 weeks later to confirm PD by iRECIST, per Investigator assessment.

If repeat imaging does not confirm PD per iRECIST, as assessed by the Investigator, and the subject continues to be clinically stable, study treatment may continue and follow the regular imaging schedule. If PD is confirmed, subjects will be discontinued from study treatment.

If a subject has confirmed radiographic progression (iCPD) as defined in **Section 12.2**, study treatment should be discontinued; however, if the subject is achieving a clinically meaningful benefit, an exception to continue study treatment may be considered following consultation with Merck. In this case, if study treatment is continued, tumor imaging should continue to be

## Proprietary Information of MD Anderson

Protocol # 2016-0251

Date: February 24, 2020

94

performed following the intervals as outlined in Section 6 and submitted to the central imaging vendor.

A description of the adaptations and iRECIST process is provided in Section 12.2, with additional details in the iRECIST publication [Seymour et al, 2017]. A summary of imaging and treatment requirements after first radiologic evidence of progression is provided in Table 11 and illustrated as a flowchart in Figure 2.

Table 11 Imaging and Treatment After First Radiologic Evidence of Progressive Disease

	Clinically Stable		Clinically Unstable	
	Imaging	Treatment	Imaging	Treatment
First radiologic evidence of PD by RECIST 1.1	Repeat imaging at 4 to 8 weeks to confirm PD.	May continue study treatment at the Investigator's discretion while awaiting confirmatory tumor imaging by site by iRECIST.	Repeat imaging at 4 to 8 weeks to confirm PD per Investigator's discretion only.	Discontinue treatment
Repeat tumor imaging confirms PD (iCPD) by iRECIST per Investigator assessment	No additional imaging required.	Discontinue treatment (exception is possible upon consultation with Merck).	No additional imaging required.	Not applicable
Repeat tumor imaging shows iUPD by iRECIST per Investigator assessment	Repeat imaging at 4 to 8 weeks to confirm PD. May occur at next regularly scheduled imaging visit.	Continue study treatment at the Investigator's discretion.	Repeat imaging at 4 to 8 weeks to confirm PD per Investigator's discretion only.	Discontinue treatment
Repeat tumor imaging shows iSD, iPR, or iCR by iRECIST per Investigator assessment.	Continue regularly scheduled imaging assessments.	Continue study treatment at the Investigator's discretion.	Continue regularly scheduled imaging assessments.	May restart study treatment if condition has improved and/or clinically stable per Investigator's discretion. Next tumor imaging should occur according to the regular imaging schedule.

Abbreviations: iCPD=iRECIST confirmed progressive disease; iCR=iRECIST complete response; iRECIST=modified Response Evaluation Criteria in Solid Tumors 1.1 for immune-based therapeutics; iSD=iRECIST stable disease; iUPD=iRECIST unconfirmed progressive disease; PD=progressive disease; RECIST 1.1=Response Evaluation Criteria in Solid Tumors 1.1.

Note: If progression has been verified, further management is by the site, based on iRECIST. Any further imaging should still be reviewed. If RECIST 1.1 disease progression has not been verified, ideally the site should continue treatment. Whether or not treatment continues, imaging should be collected and reviewed.

# Proprietary Information of MD Anderson

Protocol # 2016-0251

Date: February 24, 2020

96

[figure not shown]

Figure 2 Imaging and Treatment for Clinically Stable Subjects Treated with Pembrolizumab after First Radiologic Evidence of PD Assessed by the Site

Abbreviations: iRECIST = modified Response Evaluation Criteria In Solid Tumors 1.1 for immune-based therapeutics; PD = progressive disease; RECIST = Response Evaluation Criteria In Solid Tumors.

### 7.1.4.2 Assessment of Viral Load

#### 7.1.4.2.1 Measurement of HCV RNA

HCV-RNA levels in plasma will be measured using the Roche COBAS® AmpliPrep/COBAS TaqMan HCV Test, v2.0 on blood samples drawn from each subject at various time points prior to, during, and after dosing, as indicated in the Study Flow Chart (Section 6.0). Samples are collected and processed as per instructions provided.

Results from the sample collected at the screening visit are used to determine eligibility. Samples collected at other time points are used for efficacy analyses. They are also used to identify subjects who meet HCV virologic failure criteria. The nomenclature detailed in Table 12 will be used when describing HCV RNA levels.

Table 12 Nomenclature for Describing HCV RNA Levels

Abbreviation	Definition	HCV RNA level
TND	Target not detected	HCV RNA not detected
TD(u)	Target detected but unquantifiable	HCV RNA <LLOQ
TD(q)	Target detected, quantifiable	HCV RNA ≥LLOQ

Abbreviations: HCV = hepatitis C virus; LLOQ = lower limit of quantification.

The LLOQ of the COBAS test is 25 IU/mL and its limit of detection is 15·IU/mL. We define virological breakthrough to be confirmed HCV RNA concentration of at least 25 IU/mL after a previous value of less than 25 IU/mL. We define relapse as a confirmed HCV RNA concentration of at least 25 IU/mL following an undetectable (HCV RNA <15·IU/mL) the at end of treatment. For both virological breakthroughs and relapses, we defined confirmation as an HCV RNA concentration of at least 25 IU/mL from a separate blood draw repeated within 2 weeks.

#### *7.1.4.2.1.1 Definition of Efficacy Endpoints*

Efficacy will be defined at different timepoints during the trial. Specific endpoints are:

- SVR4: The subject has HCV RNA <LLOQ [either TD(u) or TND] 4 weeks after the end of all study therapy.
- SVR12: The subject has HCV RNA <LLOQ [either TD(u) or TND] 12 weeks after the end of all study therapy.
- SVR24: The subject has HCV RNA < LLOQ [either TD (u) or TND] 24 weeks after the end of all study therapy.

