# Proprietary Information of MD Anderson

Protocol # 2016-0251

Date: February 24, 2020

13

	therapy, whichever is earlier. Virologic response (sustained virologic response [SVR]) will be collected for 12 and 24 weeks after the end of all HCV study therapy.
Estimated average length of treatment per subject	Subjects will be treated for up to 2 years or 35 cycles of pembrolizumab.

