# Proprietary Information of MD Anderson

Protocol # 2016-0251

Date: February 24, 2020

16

each subject will be followed for 30 days for AE monitoring. Serious AEs (SAEs) will be collected for 90 days after the end of treatment or 30 days after the end of treatment if the subject initiates new anticancer therapy, whichever is earlier. Virologic response will be collected for 12 and 24 weeks after the end of all HCV study therapy.

This study will be conducted in conformance with Good Clinical Practices (GCP).

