### 3.1 Primary Objective(s)

- (1) **Objective: Arm A and Arm B:** To evaluate the tolerability of IV administration of pembrolizumab as second-line therapy in subjects with advanced HCC.
- (2) **Objective: Arm B:** To evaluate the efficacy of pembrolizumab in combination with Zepatier as assessed by the proportion of subjects with HCV GT1 or GT4 achieving Sustained Virologic Response 12 weeks after the end of all HCV study therapy (SVR12), defined as HCV RNA below the lower limit of quantitation (LLOQ) (either target detected unquantifiable [TD(u)] or target not detected [TND]) 12 weeks after the end of all study therapy.

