## 7.1.6.3 Treatment Period

Visit requirements are outlined in the Trial Flow Chart (Section 6.0). Specific procedure-related details are provided above in the Trial Procedures (Section 7.1 - Trial Procedures).

Subjects are eligible for up to 35 cycles (approximately 2 years) of treatment on pembrolizumab.

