## 8.13 Statistical Analysis of HCV Endpoints

### 8.13.1 HCV endpoints

#### 1. Primary endpoint

**Objective:** To evaluate the efficacy of pembrolizumab in combination with Zepatier as assessed by the proportion of subjects with HCV GT1 or GT4 achieving Sustained Virologic Response 12 weeks after the end of all HCV study therapy (SVR12), defined as HCV RNA below the lower limit of quantitation (LLOQ) (either target detected unquantifiable [TD(u)] or target not detected [TND]) 12 weeks after the end of all study therapy.

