# Proprietary Information of MD Anderson

Protocol # 2016-0251

Date: February 24, 2020

149

Abbreviation/Term	Definition
PK	Pharmacokinetic
PO	Oral Administration
PP	Per Protocol
PR	Partial Response
qday	Once Daily
RAV	Resistance-Associated Variants
RBV	Ribavirin
RECIST	Response Evaluation Criteria in Solid Tumors
RNA	Ribonucleic Acid
Q12W	Every 12 Weeks
Q2W	Every 2 Weeks
Q3W	Every 3 Weeks
Q9W	Every 9 Weeks
SAE	Serious Adverse Events
SD	Stable Disease
SIM	Site Imaging Manual
SOP	Standard Operating Procedures
SVR	Sustained Virologic Response
SVR4	Sustained Virologic Response 4 weeks after the end of all study therapy: The subject has HCV RNA <25 IU/mL (either TD(u) or TND) 4 weeks after the end of all study therapy
SVR12	(Sustained Virologic Response 12 weeks after the end of all study therapy): The subject has HCV RNA <25 IU/mL (either TD(u) or TND) 12 weeks after the end of all study therapy
SVR24	(Sustained Virologic Response 24 weeks after the end of all study therapy): The subject has HCV RNA <25 IU/mL (either TD(u) or TND) 24 weeks after the end of all study therapy
Tbil	Total Bilirubin
TCR	T Cell Receptor
TD(u)	Target Detected but Unquantifiable
TD(q)	Target Detected, Quantifiable
TIL	Tumor-Infiltrating Lymphocytes
TND	Target NOT detected (HCV RNA not detected)
Treg	Regulatory T Cells
TSH	Thyroid Stimulating Hormone
TTP	Time to Progression
ULN	Upper Limit of Normal
US	United States

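### The primary SVR12 endpoint has two time origins, end of HCV therapy and end of all study therapy, and the definition section uses only the broader one, which in Arm B includes pembrolizumab

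*Combined protocol and SAP*

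**What the plan says.** The primary objective for Arm B (Section 3.1) introduces the endpoint as "Sustained Virologic Response 12 weeks after the end of all HCV study therapy (SVR12". The same sentence then defines it as HCV RNA below the limit of quantitation "12 weeks after the end of all study therapy". Section 8.13.1 repeats that sentence as the primary HCV endpoint, with both origins.

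Four other places use only the broader origin:

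- Section 7.1.4.2.1.1, which defines the efficacy endpoints: "SVR12: The subject has HCV RNA <LLOQ [either TD(u) or TND] 12 weeks after the end of all study therapy". SVR4 and SVR24 are worded the same way.
- Section 12.6, the abbreviation list: "The subject has HCV RNA <25 IU/mL (either TD(u) or TND) 12 weeks after the end of all study therapy".
- Section 3.2, secondary objective 3.
- Section 8.13.1, secondary endpoint.

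The relapse rule in 7.1.4.2.1.2 also requires HCV RNA to return after all study therapy has ended.

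Two places date data collection from HCV therapy. Section 1.0 says that virologic response "will be collected for 12 and 24 weeks after the end of all HCV study therapy". Section 2.1 says "Virologic response will be collected for 12 and 24 weeks after the end of all HCV study therapy".

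On treatment length, Arm B receives Zepatier for 12 to 16 weeks, while Section 7.1.6.3 states "Subjects are eligible for up to 35 cycles (approximately 2 years) of treatment on pembrolizumab".

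**The concern.** The two phrases would mean the same thing if antivirals were the only treatment. In Arm B they are not. The protocol uses the term study therapy for pembrolizumab in the text on allowed pembrolizumab interruptions (Section 5.2.1.2) and in the section heading on stopping after complete response. Nowhere is the term limited to Zepatier and ribavirin.

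An analyst who takes the derivation from the section written to supply it would therefore count from the last pembrolizumab dose. Three things follow.

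- **The endpoint would depend on tumour outcome.** The time of SVR12 would vary with how long each subject stays on pembrolizumab. A later time point also allows more dropout before the assessment, and the Missing = Failure approach in Section 8.13.3 would count that dropout as virologic failure. The documents give no figure from which to size this.
- **Comparability would be lost.** Section 4.3.3.2 describes SVR12 in the Zepatier trials as measured 12 weeks after treatment stopped.
- **Relapse could be misfiled.** HCV RNA that returns after Zepatier ends, while pembrolizumab continues, does not fall after the end of all study therapy, so it would sit outside the relapse category. If on-treatment is read equally broadly, it might be labelled breakthrough.

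Arm B has about 15 subjects, so each one reclassified moves the SVR12 rate by 1/15, or about 6.7 percentage points.

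**Working it through.** **Inputs.** Zepatier lasts 12 or 16 weeks (Section 1.0 and Table 4). Pembrolizumab is given every 3 weeks (Table 3) for at most 35 treatments, about 2 years (Sections 2.1 and 7.1.6.3). The flow chart header in Section 6.1 gives 1 year or 17 cycles instead. Weeks are counted from the first dose, with no delays.

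**Check of the plan's own figure.** The 35th dose falls at (35 − 1) × 3 = week 102, and cycle 35 ends at 35 × 3 = week 105. At 52.18 weeks per year these are 1.95 and 2.01 years, which agrees with the stated 2 years.

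**SVR12 under each origin.** On the HCV clock it falls at Zepatier duration + 12. On the all-therapy clock it falls at last pembrolizumab dose + 12.

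| | 12-week Zepatier | 16-week Zepatier |
|---|---|---|
| HCV clock | 12 + 12 = week 24 | 16 + 12 = week 28 |
| All-therapy clock, 35 cycles | 102 + 12 = week 114 | week 114 |
| Gap | 114 − 24 = 90 weeks | 114 − 28 = 86 weeks |
| All-therapy clock, 17 cycles | 16 × 3 + 12 = week 60 | week 60 |
| Gap | 60 − 24 = 36 weeks | 60 − 28 = 32 weeks |

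If the last pembrolizumab dose comes before the last Zepatier or ribavirin dose, the two origins coincide and the gap is zero. Counting to the end of cycle 35 instead of its dose adds 3 weeks (93 or 89).

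**Scheduled draws on the all-therapy clock.** The HCV viral load row of the flow chart is marked at screening, at each cycle column, at discontinuation, at virologic failure and at the 30-day safety visit. It is not marked at the Q9W or survival follow-up visits. The last routine draw is therefore 30/7 = 4.3 weeks after the last dose. Nothing is scheduled at 12 or 24 weeks after it.

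**Scheduled draws on the HCV clock.** SVR24 falls at 12 + 24 = week 36 or 16 + 24 = week 40. Footnote q limits testing to screening and the first 8 cycles. Cycle 8 starts at 7 × 3 = week 21 and ends at week 24, and the flow chart labels that column week 24. Footnote q can thus reach SVR12 for the 12-week regimen at best. It does not reach week 28 (SVR12, 16-week regimen) or weeks 36 to 40 (SVR24). The column for cycle 8 and later is marked, which may cover subjects still on pembrolizumab. A subject who has stopped all treatment has nothing scheduled after the 30-day visit.

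**The case against.** The best reply is that the intent is plain. Sections 1.0 and 2.1 collect virologic response from the end of HCV therapy. Exploratory objective 7 (Section 4.1) counts from the end of 12 to 16 weeks of combination dosing. Section 2.1 judges virologic response 4 weeks after Zepatier stops. Footnote q expects the first 8 cycles to yield SVR data, which is impossible on a clock that may run to week 102. Section 7.1.4.2.1.1 itself sits within a part of the protocol devoted to HCV RNA.

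This stands as evidence of intent, and it settles which origin to keep. It does not remove the conflict: the primary-endpoint sentence carries both origins, and the section that defines the endpoint carries only the unintended one.

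It is also fair to say that 90 weeks is the far end. The only second-line median PFS figures in the documents, 3.1 months for regorafenib and 1.5 months for placebo (Section 4.2.1.1), suggest that many gaps could be much shorter. No pembrolizumab figure is given.

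A reader might infer more than the documents support in three ways.

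- **That SVR12 would be unobserved for most subjects.** This needs a distribution of pembrolizumab duration, and the documents give none.
- **That relapse would be judged 12 or 24 weeks after the last pembrolizumab dose.** Section 7.1.4.2.1.2 gives relapse no fixed time point, and Section 7.1.4.2.1 words it from the end of treatment. Only the start of the relapse window is affected.
- **That rewording alone is enough.** The sampling check shows that the intended clock is not fully scheduled either.

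**Conclusion.** The primary SVR12 definition is internally contradictory and, in Section 7.1.4.2.1.1, wrong as written for Arm B. The intended origin can be recovered from the rest of the protocol, so this is a definition to correct before database lock. It is not evidence that the trial plans to measure SVR12 two years out.

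The 90- or 86-week gap assumes all 35 cycles, no interruptions and a full Zepatier course. Pembrolizumab interruptions or early Zepatier stopping could lengthen it. The 17-cycle and 35-cycle statements are a separate contradiction that must also be reconciled, but the SVR12 conflict exists under either. How many subjects would be affected cannot be derived from the documents.

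**What to change.** Use one origin, the end of all HCV study therapy, stated as the last dose of Zepatier or ribavirin, whichever is later. Apply it to SVR4, SVR12, SVR24 and relapse in Sections 3.1, 3.2 (objective 3), 7.1.4.2.1.1, 7.1.4.2.1.2, 8.13.1 and 12.6. In 7.1.4.2.1.2, tie the on-treatment and end-of-treatment wording to HCV therapy as well.

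Then align the flow chart and footnote q with the 12- and 24-week collection that Sections 1.0 and 2.1 already promise. The HCV RNA draws should be dated from the last HCV dose and apply whether or not the subject is still on pembrolizumab.

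The cost is an amendment to the wording plus a small number of scheduled blood draws. Sample size and analysis method do not change.
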